2.2. Safety

All adverse events were collected, coded and reported, for the duration of the study according to the definitions of “Clinical investigation of medical devices for human subjects -Good clinical practice” ISO: 14155: 2011.

The occurrence rate for all the clinical events defined below [referred to as adverse events of special interests (AESIS)] will be calculated for each cohort, characterized by the Data Safety Monitoring Board (DSMB) and compared between and within arms (where applicable) for the duration of the study. In addition, specific events within this list will also be reported as event rates within specific time frames post procedure.

The assessment of safety was based primarily on the frequency of serious adverse device effects (SADEs) serious adverse events (SAEs), adverse device effects (ADEs), adverse events(AEs) and laboratory abnormalities classified by Investigators as related to the RDN and confirmed by the DSMB. Occurrence and frequency of SADEs and ADEs and AE(s) and SAE(s) was summarized by treatment group at baseline, last visit and by changes from baseline to last visit for laboratory values. Other safety data were summarized as appropriate.

The RDN-CKD Study DSMB is comprised of independent experts in hypertension, interventional radiology or cardiology and biostatistics. The DSMB was responsible for the oversight, review of all relevant SAEs including but not limited to:

- All unanticipated events

- All events pre-specified as part of the overall safety assessment
- All device- or procedure-related events (ADEs and SADEs)
- Deaths

During the course of the study, the DSMB reviewed accumulating safety data blinded to subject randomization in order to monitor the incidence of protocol-defined events and other trends that would warrant modification or termination of the study. Responsibilities, qualifications, membership, and committee procedures were outlined in the DSMB Charter.

All safety aspects mentioned in chapter 1.1.5 will be listed and compared between RDN and sham group.

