1.2. Design of the Trial

RDN-CKD Study is a prospective, randomized (1:1, central randomization), double-blind (unblinded interventionalist and blinded study team at each center), sham controlled, multicenter feasibility study. All centers have participated at least in one of the sham-controlled trials in primary hypertension thereby having established an unblinded and a blinded team.

The RDN-CKD Study has been conducted at 5 clinical investigational sites, which are the University Hospitals in Erlangen, Homburg/Saar, Düsseldorf, Berlin and Nürnberg.

We aimed to include 80 patients with CKD stages 3a or 3b (according to the currently used estimation formulas [MDRD, CKD-EPI] and uncontrolled hypertension in the RDN-CKD study. This number of patients could not be achieved due to diverse reasons (pandemic, low recruitment). Therefore the recruitment got stopped by 31.12.2022.

If the patient fulfils inclusion criteria and in the absence of exclusion criteria at visit 1, the patient has been enrolled into the trial, and the study visits were scheduled. All subjects have their office BP measured, a limited medical history review, physical exam and current medication review and a safety laboratory evaluation. Furthermore, an ABP measurement was conducted. Visit 2 serves a FU in the run-in phase. All subjects were checked for medication adherence. A 24-h ambulatory BP measurement was conducted. Additionally, all subjects had their office BP measured, physical exam and current medication review and a safety laboratory evaluation. Once a subject has met all the screening criteria for the study the visit was scheduled for the renal angiogram and RDN/Sham procedure. Subjects of child bearing potential must have a documented negative pregnancy test dated within a maximum of 7 days prior to the procedure.

Randomization occurred following the diagnostic renal angiogram. Only randomized patients counted towards the enrollment ceiling. FU Visits took place 3 weeks, 6 weeks, 12 weeks, 19 weeks, 26 weeks, 39 weeks, 52 weeks post procedure. All baseline measurements were repeated 12 weeks, 26 weeks and 52 weeks post-procedure. Due to early recruitment stop of the study certain number of patients had only FU visits till 26 weeks post procedure.

Escape Criteria

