2.7.3. Efficacy measures

2.7.3.1. Primary and secondary efficacy variables

Office Blood Pressure Measurements

The measurement of office BP was done according the following guidelines based on the 2018 ESH/ESC Guidelines for the management of arterial hypertension. [5]

24-h ambulatory BP Measurements

The measurement of 24-h ambulatory BP will occur at -4, -1, 12, 26, and 52 weeks FU visits with the ambulatory BP system (Mobilograph®, I.E.M. Stolberg, Germany; 90207 or 90217A, Spacelabs Healthcare, Meerbusch, Germany). Only ambulatory BP recordings with a minimum of 28 measurements during the 24 hour period will be considered valid. The measurement of ambulatory BP was done according the following guidelines based on the 2018 ESH/ESC Guidelines for the management of arterial hypertension. [5]

Home BP Measurements

Home BP measurements are introduced to increase safety for the patients, not for efficacy. After education on the use of the Home BP system, all subjects will be provided with a Home BP monitor (apnorm® Professional Touch, microlife, Widnau, Switzerland).

eGFR Calculation

eGFR calculations for inclusion will be standardized using the currently used estimation formulas (MDRD, CKD-EPI).

Laboratory Assessments

All subjects will have blood collected at every visit. In addition, all subjects will have urine samples collected at -4, -1, 12, 26, and 52 week follow-up visits for urine analysis. Females of child bearing potential will have a urine or blood plasma pregnancy test up to 7 days prior to the procedure.

Laboratory Data	
Blood Chemistry	urea, creatinine, eGFR, cystatin C, uric acid, sodium, potassium, calcium, γ -GT, GOT, GPT, alkaline phosphatase, total cholesterol, LDL-cholesterol, HDL-cholesterol, triglycerides, total serum protein Fasting blood glucose, HbA1c
Hematology	hemoglobin, hematocrit, erythrocyte count, platelet count, white blood count
Urin analysis	Spot urine (urinary creatinine, protein, albumin, sodium and potassium), Urine pregnancy testing (applicable females only)

HP LC-MS/MS of Antihypertensive Adherence

HP LC-MS/MS is a recognized method with good to excellent sensitivity and specificity to detect many pharmacological agents in urine. Urine collected at -1 and 26 and 52 weeks FUs will be sent for analysis.

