2.9. General Analysis

2.9.1. General Methodology

Descriptive statistics will be displayed for all documented and derived variables. For continuous variables, number of observations, number of missing values, mean, standard deviation, minimum, median and maximum will be calculated. For categorical variables, number of patients, absolute and relative frequencies will be calculated.

In this parallel, controlled study, data analysis will be performed using unadjusted analysis, i.e. simple paired and unpaired t-test under the assumption of a normal distribution for the difference of interest.

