2.9.5.2. Criteria for clinically notable laboratory abnormalities

Please note: Normal ranges are given by the central laboratory of the University Hospital Erlangen-Nuremberg

Liver parameters:

Serum SGOT, SGPT, γ -GT, AP > 30% of upper normal range

Renal parameters:

decrease of eGFR (CKD-Epi) >30%, serum potassium above normal range, serum sodium under normal range

Hematological parameters:

Abnormal blood cell counts at baseline and changes of $\geq 20\%$ of blood cell counts

Descriptive statistics of all laboratory values will be given.

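### SAP 2.2 counts laboratory abnormalities only if judged RDN-related, and its by-arm laboratory summary uses only baseline and a last visit that differs between patients

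*SAP*

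**What the plan says.** Section 2.2 says safety was assessed primarily on a list of device effects, adverse events and "laboratory abnormalities classified by Investigators as related to the RDN and confirmed by the DSMB". The qualifier may govern the whole list or only its last item. On either reading it governs laboratory abnormalities.

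The same section gives one laboratory summary split by arm: "summarized by treatment group at baseline, last visit and by changes from baseline to last visit for laboratory values". It does not define the last visit. Section 1.2 states that because of the recruitment stop a "certain number of patients had only FU visits till 26 weeks post procedure"; the others were followed to week 52.

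Section 2.9.5.2 sets thresholds for liver enzymes and blood counts, and for renal parameters: "decrease of eGFR (CKD-Epi) >30%, serum potassium above normal range, serum sodium under normal range". These carry no relatedness condition. The output stated there is "Descriptive statistics of all laboratory values will be given". Section 2.9.1 adds a general rule: "For categorical variables, number of patients, absolute and relative frequencies will be calculated".

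Under Laboratory Assessments, section 2.7.3.1 says "All subjects will have blood collected at every visit", so the intermediate values exist.

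**The concern.** A 1:1 randomised sham control lets the arms be compared on everything that happened, whatever its cause. That comparison needs no opinion on causality. Section 2.2 instead applies such an opinion to laboratory abnormalities, with a second confirmation by the DSMB, before they count towards the primary safety basis. The causality scale in section 2.8 has five levels, and the SAP does not say which of them count as related.

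The by-arm laboratory summary does not make up for this. It looks at one follow-up time per patient, and that time differs between patients. An abnormality that appears and resolves between baseline and the last visit leaves no trace in it.

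At stake is how visible a few individual events are, such as hyperkalaemia, in patients with CKD stage 3 in a trial whose objective includes verifying safety. No efficacy result depends on it.

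**Working it through.** The SAP gives no figure to reproduce. The check follows the data through the stated analyses.

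**Visits available.** Section 1.2: "FU Visits took place 3 weeks, 6 weeks, 12 weeks, 19 weeks, 26 weeks, 39 weeks, 52 weeks post procedure". That is 7 scheduled follow-up visits, of which 5 (weeks 3, 6, 12, 19 and 26) are common to both follow-up lengths. The by-arm summary in 2.2 uses the last one only.

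**Case A: potassium above range at week 6, normal at baseline and at the last visit.**

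| Route in the SAP | Does the event appear by arm? |
|---|---|
| 2.2, related laboratory abnormalities | Only if judged RDN-related and confirmed by the DSMB |
| 2.2, by-arm laboratory values | No: normal at both times used |
| 1.1.2, secondary endpoints | No: serum potassium is not listed |
| 1.1.5, AESI and major adverse events | No: there is no potassium item |
| 1.1.5, AE comparison | Yes, if it was recorded as an AE |
| 2.9.5.2 with 2.9.1 | It meets a criterion and can be counted as a derived categorical variable; the arm split is not stated |

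The same trace applies to sodium, liver enzymes and blood counts. None has its own item in 1.1.2 or among the AESI and major adverse event definitions of 1.1.5.

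**Case B: a fall in eGFR.** Section 1.1.2 compares the change in creatinine, cystatin C and eGFR between arms at all time points. Section 1.1.5 adds the early creatinine/eGFR comparison and the renal AESIs. Renal change is therefore already compared by arm regardless of cause. Only the count of patients with a fall of more than 30% is not stated by arm.

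**The AE route.** The AE definition in 2.8 includes abnormal laboratory findings whether or not device-related, and 1.1.5 compares AE numbers by arm. However, 2.8 describes the laboratory values on the AE form as clinically relevant ones and applies no fixed threshold. The route therefore works for abnormalities that an investigator chose to record.

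**What the filter does under blinding.** Let p(R) and p(S) be the proportions of patients with an abnormality under RDN and sham. Let q be the probability that an abnormality is judged related and confirmed. Assume q is the same in both arms, as blinded judgement would suggest. The counted proportions are q·p(R) and q·p(S).

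- Difference: q·[p(R) − p(S)], which shrinks by the factor q.
- Ratio: q·p(R) / [q·p(S)] = p(R)/p(S), which is unchanged.
- Number of events: reduced by the factor q.

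The filter therefore costs events and makes the absolute difference smaller. It does not by itself favour an arm. The SAP gives no value for p(R), p(S) or q, so the loss cannot be quantified.

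**The case against.** The strongest reply is that the trial is blinded. Section 1.2 describes a blinded study team, the AE record in 2.8 does not reveal the device, and 2.2 says the DSMB reviewed safety data without knowing allocation. A reader might infer that the relatedness filter biases the safety comparison. The documents do not support that: a judgement made without knowledge of the arm loses sensitivity in both arms. If investigators recognise true device effects better than chance, the filter could even concentrate the signal. This part of the reply stands. What remains is that events are discarded without need.

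A reader might also infer that the plan has no all-cause, by-arm laboratory safety analysis. That goes too far, because the AE, SAE, AESI and major adverse event comparisons and the renal markers carry no causality filter.

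Nor should section 2.9.5.2 be read as omitting counts altogether. Meeting a criterion is naturally a derived categorical variable, and 2.9.1 gives frequencies for those. The missing arm split is a matter of detail in a study that 2.9.1 itself describes as parallel and controlled.

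Finally, it is tempting to express the gap as the share of follow-up visits outside the by-arm summary. That would count visits for which the arm split is not spelled out. It would not count visits left unanalysed: 2.9.5.2 promises statistics of all laboratory values, and 2.2 leaves other safety data to be summarised as appropriate.

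None of this changes the rule that 2.2 does state, or the two times its by-arm summary uses.

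**Conclusion.** The point holds in limited form and is minor. Section 2.2 makes relatedness a condition for laboratory abnormalities where an all-cause comparison is available and better suited to a sham-controlled trial. Its by-arm laboratory summary also mixes week 26 and week 52 and can miss transient abnormalities. The practical gap is potassium, sodium, liver enzymes and blood counts that were out of range at an intermediate visit and were not recorded as AEs.

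The effect on conclusions is unknown, because the SAP gives no event rates. Section 2.4 makes the analysis exploratory and descriptive, so simple counts are enough. The conclusion assumes that blinding held for the relatedness judgements, and that the last visit means each patient's final scheduled visit.

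**What to change.** In section 2.2, remove the condition of investigator-judged relatedness and DSMB confirmation for laboratory abnormalities.

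In section 2.9.5.2, add: *For each criterion, the number and percentage of randomised, treated patients who newly meet it at any post-procedure visit up to week 26 will be shown by arm, regardless of causality, and separately up to week 52.*

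Three details belong with it:

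- **Baseline condition.** Newly means not met at the pre-procedure visit; alternatively, show baseline status in a shift table. CKD stage 3 patients may already be outside a limit such as potassium before the procedure, and counting them would mix old with new abnormalities.
- **Population.** The safety population in 2.3 is everyone who consented, which can include patients who were never assigned an arm. Hence randomised, treated patients. State the denominator of the week 52 table, since some patients were followed only to week 26.
- **Supportive table.** Keep abnormalities judged related in a supportive table, and say which of the five causality levels count.

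The cost is a wording change and one extra table from laboratory data already collected. The downside is higher counts in both arms than a related-only table would show.

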2.3. Analysis populations

For the analyses of the study, following populations are pre-specified:

1. The **Safety population (SAF population)** included all patients who provided informed consent
2. The **Intention-to-treat population (ITT population)** consisted of all randomised patients having a post-procedure measurement of at least one (primary) efficacy parameter.
3. The **modified ITT population (mITT)** include only participants from the ITT population without adherence violations.
4. The **Per Protocol population (PPP)** included all patients of the ITT population who did not show any major protocol violation (defined prior to unblinding of the data). These patients received at least two measurements of 24-h ambulatory BP (one pre-procedure (week -4 or week -1) and one 3 or 6 months post-procedure), performed in technically high quality.
5. The **Modified Per Protocol Population (mPPP)** include only patients of the PPP without adherence violations
6. The **Bavarian population** include only patients from 2 centres (Erlangen and Nürnberg)

Use of analysis sets

Demographic data and clinical characteristics of the patients will be displayed on all the pre-specified populations. Prior and concomitant medications as well as prior and concomitant medical conditions will be reported on all pre-specified populations.

The ITT population will be the basis for the primary analysis.

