2.4. Analyses

Statistical analyses will be based on the basis of international guidelines (CPMP/ICH/363/96:E9). Due to the early stop of the study, only an exploratory and descriptive analysis takes place. Statistical methods used to compare groups for primary and secondary outcomes:

Efficacy: Change of systolic 24-h ambulatory BP at 6 months post-procedure (primary efficacy endpoint) compared between the RDN and sham group will be analyzed in a linear mixed model including the covariates that were significantly different between the groups at baseline. All secondary (see 1.1.2) and observational endpoints (1.1.3 and 1.1.4) are analyzed also via a modelling approach adjusting for potential imbalances in baseline characteristics. The type I error for the analysis of the primary endpoint is set at 5% (two-sided), all analyses of secondary endpoints have an exploratory character avoiding multiplicity issues in this trial.

In addition, a win ratio analysis will be conducted, with the criteria 24h ambulatory systolic BP change > 5 mmHg, office systolic BP change > 10 mmHg, and decrease of medication as defined by following 3 parameters (number of antihypertensive drugs, drug burden index and antihypertensive load index).

Analysis will be performed for the following populations:

1. Primary analysis is based on *the intention-to-treat* (ITT) population consisting of all randomized study subjects that are all either RDN treated or sham treated.
2. A secondary analysis will be done with a *modified ITT* population (mITT) in which participants with adherence violations will be excluded (sensitivity analyses).
3. A secondary analysis will be done with the *per protocol population* (PPP) in which study subjects with predefined protocol deviations (defined prior to unblinding of the data) are excluded.
4. A secondary analysis will be done with the modified *per protocol population* (mPPP) in which study subjects of the PPP with adherence violation are excluded.
5. A secondary analysis will be done with the safety population (SAF) in which all study subjects signing informed consent are included.

6. A secondary analysis will be done with those patients that are investigated by the Erlanger and Nürnberger center (CRC staff), with a total of N=20 randomized patients (Bavarian cohort)

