2.7. Definition of Derived Variables and Transformation of Variables

2.7.1. Missing Values

Missing values in the CRF documented as “ND”, “NA” or “UNK” will usually not be entered into the database and the field will be blank.

If date parts are missing (the ‘day’ and/or the ‘month’) and there are calculations needed, a missing day will be replaced by ‘01’, a missing month will be replaced by ‘01’. A missing year will not be replaced.

In case of the start date of an AE is missing, the date of first treatment intake (if appropriate) will be used as worst case imputation, otherwise the first day/month instead of the middle will be taken also as a worst case imputation.

Data of patients having withdrawn their consent to study participation at any time point during the study were not accounted for in the respective analyses up to the time point of withdrawal.

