2.9.5.1. Adverse Events

Frequency tables for the preferred terms will be compiled, based on patients experiencing an AE and based on the number of AEs. The AE will also be analysed with regard to system organ class. They will be displayed with regard to severity and relationship to study drug. All AEs will be listed.

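### The SAP names two unranked methods for the primary test, leaves a missing week-26 ABP unaddressed, words the consent-withdrawal rule so that it discards valid data, and defines ITT in two ways.

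*SAP*

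**What the plan says.** **Primary method.** SAP 2.4 states that the change in 24-h systolic ABP at 6 months "will be analyzed in a linear mixed model including the covariates that were significantly different between the groups at baseline". Section 2.9.1 states that "data analysis will be performed using unadjusted analysis, i.e. simple paired and unpaired t-test". Section 2.9.4.1 then names the unpaired t-test for the primary null hypothesis, introduced as an example. Sections 2.4 and 2.9.4.1 both keep a two-sided 5% level.

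**Baseline.** Section 1.1.1 lists two reference values for the primary endpoint: P (mean of weeks -4 and -1) and B (week -1 only).

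**Withdrawal.** Section 2.7.1 says that data of patients who withdrew consent "were not accounted for in the respective analyses up to the time point of withdrawal". It gives rules for incomplete dates but none for a missing efficacy value.

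**Safety set and listings.** In 2.3 the safety population "included all patients who provided informed consent". Section 2.9.5.1 says "All AEs will be listed".

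**ITT, the set for the primary analysis.** In 2.3 it "consisted of all randomised patients having a post-procedure measurement of at least one (primary) efficacy parameter". In 2.4 it is the "population consisting of all randomized study subjects that are all either RDN treated or sham treated". Section 2.9.3 confines enrolled but untreated patients to listings.

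**The concern.** The primary endpoint is the one endpoint for which the SAP sets a type I error, so its method and analysis set should be readable in one way only. An adjusted mixed model and an unadjusted t-test can give different estimates and p-values on the same data. The model's covariates are to be those that differ significantly between the arms at baseline, so they cannot be listed until the arms have been compared. A small trial that stopped early has little room for such choices.

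The withdrawal sentence matters for another reason. If a programmer follows it as written, valid blood pressure values and adverse events leave the analysis. The ITT wording matters least, but mITT, PPP and mPPP are all built from ITT, so two definitions lead to two sets of denominators throughout the report.

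**Working it through.** There is no stated figure to reproduce: the SAP gives no effect size, SD, power, dropout rate or total randomised. The check is mainly a comparison of the sections.

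**1. Who contributes to the primary comparison.** ABP is scheduled at weeks -4, -1, 12, 26 and 52 (2.7.3.1). Section 2.4 gives the outcome as the 6-month change and names no other visit, random effect or covariance. The model can therefore be read in two ways. In the last column baseline is a covariate.

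| Post-procedure ABP available | t-test on 6-month change | 2.4 model, 6-month change only | 2.4 model, weeks 12 and 26 |
|---|---|---|---|
| Week 26 present | in | in | in |
| Week 12 only | out | out | in |
| None | out | out | out |

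The two methods differ on a missing week-26 value only under the last column, and the SAP does not say whether that column applies. The middle row is not hypothetical: the PPP definition in 2.3 accepts a patient whose only post-procedure ABP is at 3 months. The ITT definition in 2.3 could do so too, since the bracketed word leaves open which measurement qualifies.

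**2. How many primary results the text allows.** Two methods x two baselines (P, B) = 4 in the ITT population, before any choice of covariates.

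**3. The withdrawal rule read literally.** After withdrawal there are normally no further data. A rule that leaves out data up to withdrawal therefore removes what exists and spares what does not. A patient who withdraws between weeks 26 and 52 would lose a week-26 primary value already recorded. The adverse events would go as well, although that patient belongs to the safety set by having consented, and 2.9.5.1 lists every event.

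The leverage of one removed value can be shown by arithmetic. Let an arm have n patients with mean m, and let one patient lie d from m. The mean of the rest is (n x m - (m + d))/(n - 1) = m - d/(n - 1). The arm difference moves by the same amount. The values of d are assumptions.

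| n per arm | d = 5 mmHg | d = 10 mmHg | d = 15 mmHg |
|---|---|---|---|
| 40 (target of 80 at 1:1, not reached) | 5/39 = 0.13 | 10/39 = 0.26 | 15/39 = 0.38 |
| 20 (assumed, half the target) | 5/19 = 0.26 | 10/19 = 0.53 | 15/19 = 0.79 |
| 10 (secondary Bavarian cohort, N=20, even split assumed) | 5/9 = 0.56 | 10/9 = 1.11 | 15/9 = 1.67 |

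This is the effect of one lost value. It is not an estimate of bias in this trial.

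**4. The two ITT definitions.** A treated patient with no post-procedure measurement is in the 2.4 set and not in the 2.3 set. By the last row of the first table that patient adds nothing to the week-26 estimate by any of the three routes, so only the reported count changes.

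**5. Timing.** Recruitment stopped by 31.12.2022 (1.2). Visit 1 is at week -4, so week 26 falls 30 weeks (210 days) after it, on about 29.07.2023 for a patient enrolled on the last day. The SAP is dated 01.09.2023. The flow sheet notes tie unblinding to the 6-month data being entered and secured, but the SAP does not say whether it had taken place.

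**The case against.** **The analysis is exploratory.** Section 1.2 calls this a feasibility study, and 2.4 says that after the early stop the analysis is exploratory and descriptive. That lowers the stakes. It does not reconcile the sections, since both 2.4 and 2.9.4.1 keep a 5% test. Nor does the example wording in 2.9.4.1 settle the matter, because 2.9.1 prescribes t-tests without that qualifier.

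**The methods may not differ on missing data.** This objection stands. A reader might infer that the t-test drops patients whom the mixed model keeps, and might then attach a bias in mmHg to the difference. The SAP does not support this. Section 2.4 models only the 6-month change, and on that reading both methods drop the same patients. A simulation of a two-visit model would test a model that the SAP does not describe, on wholly assumed inputs.

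**The withdrawal sentence is a slip.** Very likely it is, and nothing shows that data were in fact discarded. Section 2.2 states that "All adverse events were collected, coded and reported, for the duration of the study"; that concerns collection and reporting, and does not strictly contradict an exclusion from analyses. The conflict with the safety set in 2.3 and the listing in 2.9.5.1 remains, and the SAP has no other rule for withdrawal of consent.

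**The ITT point is minor.** This too stands. A reader might infer that the condition in 2.3 biases the primary estimate, but a patient without any post-procedure ABP adds no outcome under either wording.

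**Escape.** Section 1.2 says that subjects who meet the escape criteria are to be excluded. A reader might infer that they leave ITT. Neither ITT definition says so, and 1.1.5 compares escape rates between arms. What the exclusion covers may be settled in the protocol, so only the wording needs reconciling.

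**Conclusion.** The point holds as a matter of specification and should be fixed. The main defect is that one primary test has two unranked methods, with covariates left to baseline significance tests and no statement of which visits the model uses. The second is a withdrawal rule that gives a wrong result if followed literally. The differing ITT definitions are a lesser, denominator-only matter.

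No size or direction of bias can be derived from the SAP. What can be stated is that the text permits at least four primary results in ITT, and that one wrongly removed value 15 mmHg from its arm mean would move that mean by 0.38 mmHg with 40 per arm and by 0.79 mmHg with 20 per arm. The 15 mmHg and the 20 per arm are assumptions. The conclusions on method, withdrawal and ITT rest on the text alone.

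**What to change.** 1. **Primary method (2.4, 2.9.1, 2.9.4.1).** Name one: the mixed model fitted to week-12 and week-26 24-h systolic ABP, with one pre-named baseline value (P or B) as covariate and the RDN-sham contrast at week 26. State the covariance and the visit terms. Fix any further covariate in advance and drop the selection by baseline significance. Keep the t-test as supportive. If unblinding has already taken place, report both methods and say so.
2. **Withdrawal (2.7.1).** State that data collected up to withdrawal are kept in the efficacy and safety analyses as far as consent allows, and that only later data are absent.
3. **ITT (2.3, 2.4).** Use one definition with no condition on a post-procedure measurement, and reconcile it with the listings-only rule of 2.9.3 for patients not treated.
4. **Missing data.** Report missing week-26 ABP by arm. Sections 2.9.1 and 2.9.2 already provide counts of missing values and reasons for discontinuation, so this is one further table. The two-visit model helps only where loss depends on observed values; a sensitivity analysis that shifts the missing values is a reasonable option, not a requirement.
5. **Escape (1.2).** Reconcile the exclusion wording with the ITT definition. No view is taken on the clinical rule.

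The cost is wording in the sections named and one by-arm table. No new data are needed.
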